6.2.2 Guideline for Managing Hypoglycemic Risks

The following guideline is provided for minimizing hypoglycemic risks during the study. The treating physicians should exercise their clinical judgment for the treatment of individual patients.

6.2.2.1 Peri-procedure

The dose of sulfonylureas or meglitinides will be reduced by 50% (or discontinued if on the lowest recommended dose) one day before the index procedure to avoid potential hypoglycemic risks. If an episode of documented or symptomatic hypoglycemia is experienced during the peri-procedure or transitional diet period, further reduction of sulfonylurea or meglitinide dose by 50% or discontinuation if on the lowest dose should occur. In the absence of hyperglycemia, sulfonylureas or meglitinides may be resumed to baseline dose when participant starts soft food (i.e. one week post procedure).

Metformin should be held the day prior to endoscopy and resumed post procedure when the patient tolerates oral intake.

SGLT2i should be held three (3) days prior to the index procedure and resumed when the patient starts soft food (i.e. one week post procedure).

GLP-1 Receptor agonists and DPP4 may be held in the peri-procedure period if the subject experiences significant nausea and/or vomiting and can be resumed once symptoms resolve at the discretion of the principal investigator.

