Study Design	
This is a multicenter, single-arm, open-label study conducted in Australia.
 
Twenty (20) participants will be enrolled initially and up to 60 participants may be enrolled in the non-insulin (NIS) Cohort. The first 30 participants will be treated with the first-generation catheter (Gen 1) and the next 20-30 participants will be treated with the second-generation catheter (Gen 2). Patients who sign the informed consent and are deemed eligible following a general and endoscopic screening will be enrolled in the study.
 
Patients with T2D inadequately controlled on 1-4 non-insulin glucose-lowering medication(s) will be screened for study eligibility. Eligible patients who consent to participate in the study will maintain his/her background anti-diabetic medication(s) stable (no medication or dose change) for at least 12 weeks prior to baseline visit.
 
The index procedure will be performed under general anesthesia or deep sedation and within 28 days from the baseline visit. Patients will undergo an endoscopic screening immediately prior to the index procedure. The index procedure will be performed under fluoroscopic and endoscopic guidance. Patients may be discharged the same day per the local hospital's guideline. A patient is enrolled in the study when an energy delivery is attempted. Patients excluded during endoscopic screening will be considered screen failure and will be followed for four weeks after the procedure for safety.
 
Post index procedure, participant will be on a transitional diet consisting of clear liquids for 24 hours followed by full liquid diet for 3 days, pureed food for 3 day, and soft food for one week.
 
Background medication(s) may be decreased peri-procedurally per Section 6.2.2 but will be titrated to the pre-procedure dose and maintained for 24 weeks post index procedure and during the transitional diet period. After the 24-week follow-up visit, participants will be managed according to the current guidelines of American Diabetes Association and their glucose-lowering medications will be optimized to

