Peri-Procedural Medications	
 Titration for Sulfonylureas and Meglitinides: 
 Dose reduction by 50% (or discontinuation if on the lowest recommended dose) starting on the day before index procedure through two-week transitional diet period post procedure. If a hypoglycemic episode is experienced (symptomatic or documented), the dose must be further reduced by 50% again or discontinued if the participant is on the lowest dose. Following the transitional diet period and a review of CGM readings, the medication will be returned to pre-procedure dose if deemed safe and appropriate by the principal investigator. Titration for other medications: 
 Metformin should be held the day prior to endoscopy and resumed post procedure when the patient tolerates oral intake. GLP-1 Receptor agonists should be held in the peri-procedure period if the subject experiences significant nausea and/or vomiting and can be resumed once symptoms resolve at the discretion of the principal investigator.

	
 ○ Generally, the dosage of other medications may remain unchanged peri-procedurally unless a hypoglycemic risk is identified by blood glucose monitoring. ● Proton Pump Inhibitor (PPI) 
 ○ Patients will be placed on PPI (Omeprazole 40 mg daily or equivalent) 1 week prior to the index procedure ● Antiemetics and antispasmodics 
 ○ Patients will be provided with antiemetics and antispasmodics on standby post procedure
Post Procedural Diet and Lifestyle Modification	
 ● Patient will be on clear liquid diet for 24 hours, followed by a full liquid diet for 3 days, pureed food for 3 days, soft food for one week, and then transitioned to normal diet as tolerated. ● Following the transitional diet period, patient will participate in monthly lifestyle modification counseling sessions to promote adherence to a diet and lifestyle suitable for diabetes.
Safety Monitoring	Safety will be monitored throughout the study. The investigators will assess the occurrence of adverse events at each follow up visit. An independent medical monitor will review and monitor the safety data throughout the study. Changes in amylase, lipase levels post procedure will be evaluated for any potential pancreatic injury.

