6.2.1 Background Glucose-Lowering Medications

Eligible participants must be on one to four non-insulin glucose-lowering medication(s) without a severe hypoglycemic event within the past six months of the screening visit.

Participant's background medication will be kept stable (no change in medication or dose) for at least 12 weeks prior to the Baseline Visit.

Peri-procedurally, the dose of medications with hypoglycemic risks will be adjusted per guidelines provided in **Section 6.2.2**.

During the transitional diet period, participant's medication will be titrated to the background level and maintained stable until the Week 24 Visit has been completed. Medication and/or dose change necessary for managing hypoglycemia, hyperglycemia, or other safety concerns is permitted. Reason for the medication change must be documented on eCRF.

Following the Week 24 Visit, participants will be managed according to the current (2020) guidelines of the American Diabetes Association² and their glucose-lowering medications will be optimized as necessary to reach an HbA1c target of 7%.

Background medications are non-investigational products. They should be used in accordance with standard of care and their approved labeling. They will not be provided by the sponsor except if required by local regulations.

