6.2.2.2 During Diet Transition Period

During the diet transition period, CGM data will be reviewed by the treating physician and used to guide medication titration.

If the risk of hypoglycemia has not been adequately reduced, doses of sulfonylureas, meglitinides, or possibly other glucose-lowering medication(s) should be further reduced or discontinued if appropriate and in the clinical judgment of the participant's treating physician.

In the event of severe hypoglycemia, study staff will document these episodes on the Adverse Event form.

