6.1.2.2. Peri-procedural Period

Peri-procedurally, metformin should be held the day prior to endoscopy and resumed post procedure when the patient tolerates oral intake. The dose of sulfonylureas or meglitinides will be reduced by 50% (or discontinued if on the lowest recommended dose) one day before the index procedure to avoid potential hypoglycemic risks. If an episode of documented or symptomatic hypoglycemia is experienced during the peri-procedure or transitional diet period, further reduction of sulfonylurea or meglitinide dose by 50% or discontinuation if on the lowest dose should occur. In the absence of hypoglycemia, sulfonylureas or meglitinides may be resumed to the baseline dose when the patient transitions to soft food (i.e. one week post procedure).

The background SGLT2i should be held three (3) days prior to the index procedure and resumed when the patient transitions to soft food (i.e. one week post procedure).

GLP-1 Receptor agonists and DPP4 may be held in the peri-procedure period if the subject experiences significant nausea and/or vomiting and can be resumed once symptoms resolve at the discretion of the principal investigator.

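### Protocol 6.2.2.1 lets sulfonylureas and meglitinides return to baseline dose in the absence of hyperglycemia, where hypoglycemia is plainly meant; one Summary row also times that return differently.

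*Protocol*

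**What the plan says.** Section 6.2.2 of the protocol is a guideline for limiting hypoglycemic risk, applied with the treating physician's judgment. Under 6.2.2.1, sulfonylureas and meglitinides are halved, "or discontinued if on the lowest recommended dose) one day before the index procedure to avoid potential hypoglycemic risks". A documented or symptomatic hypoglycemic episode in the peri-procedure or transitional diet period calls for another halving, or for stopping the drug if already at the lowest dose. The return rule follows: "In the absence of hyperglycemia, sulfonylureas or meglitinides may be resumed to baseline dose when participant starts soft food", which the section equates with one week after the procedure.

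Appendix 4, 6.1.2.2, gives the same rule for the insulin cohort: "In the absence of hypoglycemia, sulfonylureas or meglitinides may be resumed to the baseline dose when the patient transitions to soft food", also at one week.

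Other places bear on when the dose returns:

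- Section 6.2.1: "During the transitional diet period, participant's medication will be titrated to the background level".
- Section 6.2.2.2: "During the diet transition period, CGM data will be reviewed by the treating physician and used to guide medication titration".
- Protocol Summary, Peri-Procedural Medications row: the halved dose applies "starting on the day before index procedure through two-week transitional diet period post procedure", and then "Following the transitional diet period and a review of CGM readings, the medication will be returned to pre-procedure dose if deemed safe and appropriate", as judged by the principal investigator.
- Protocol Summary, Study Design row: "Background medication(s) may be decreased peri-procedurally per Section 6.2.2 but will be titrated to the pre-procedure dose", followed by loosely worded text about maintaining that dose for 24 weeks and during the transitional diet.

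Appendix 5, sections 4.2 and 4.3.2, sends peri-procedural care at re-treatment to Section 6 of the main protocol.

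**The concern.** These are the drugs that the protocol singles out for dose reduction because of hypoglycemic risk. The sentence that lets them return to full dose during a restricted diet is an operative instruction, and its condition points the wrong way. Taken at its word, it does not ask whether glucose has been low. It also withholds its permission from participants whose glucose is high, who have the clearest reason to resume. High readings are to be expected in a cohort enrolled with HbA1c of 7.5% to 11.0%, and Appendix 1 grades hypoglycemia but gives no threshold for hyperglycemia, so the literal condition is hard to apply.

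Separately, a site that works from the Summary and a site that works from Section 6.2.2.1 can return the drug on different days. At stake are participant safety and uniform background medication in the first two weeks. No endpoint definition, analysis population or statistical figure depends on it.

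**Working it through.** **1. The word.** Three comparisons, all within the protocol:

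| Place | Direction it guards against |
|---|---|
| 6.2.2, stated purpose | low glucose |
| 6.2.2.1, reason for the initial halving and trigger for the further cut | low glucose |
| 6.2.2.1, return to baseline dose | high glucose |
| Appendix 4, 6.1.2.2, return to baseline dose | low glucose |

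The third row is the only one that differs. The Appendix 4 sentence has nearly the same wording and the same timing. Replacing *hyperglycemia* with *hypoglycemia* in 6.2.2.1 makes the two cohorts agree in both condition and timing.

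**2. What the literal text would allow.** After the first cut the dose is 50% of baseline, or 0% for a participant on the lowest recommended dose. After a hypoglycemic episode it is 0.5 × 0.5 = 25% of baseline, or 0%. Taken alone, the return sentence would not exclude that participant from resuming 100% when soft food starts, because its condition mentions only high glucose. The corrected word closes that gap.

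**3. The timing.** Diet schedule from Section 6.1:

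- Clear liquids 1 day + full liquids 3 days + pureed food 3 days = 7 days. Soft food starts on day 7, which reproduces the one-week figure in 6.2.2.1.
- 7 + 7 days of soft food = 14 days. This reproduces the two-week transitional diet in the Summary.
- Gap between the earliest return in 6.2.2.1 and the earliest return in the Summary row: 14 − 7 = 7 days.

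Because 6.2.2.1 says the drug *may* be resumed, a site that waits until day 14 and reviews CGM satisfies both texts. Only a return on days 7 to 13 is allowed by one and barred by the other.

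**4. Reach of the word correction.** Section 4.1 caps the non-insulin cohort at 60, with the first 30 treated with Gen 1. The Appendix 5 introduction says Gen 2 was introduced after those 30 were enrolled. Remaining index procedures are therefore at most 60 − 30 = 30. Re-treatment is restricted to Gen 2 participants (Appendix 5, 4.1), so at most 30 participants. The insulin cohort is not affected, because Appendix 4 has its own sentence with the right word.

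These are ceilings. The Summary's Timeline row puts the end of enrollment at Q2 2023, and Version O is dated 30 Sep 2023, so few or no index procedures may remain. The documents do not give the number of Gen 2 participants already treated or the share taking these drugs.

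**The case against.** The strongest reply is that this is a self-evident slip which context already corrects. Most of that stands as a limit on harm:

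- The preceding sentence in 6.2.2.1 calls for a further cut after hypoglycemia.
- Section 6.2.2.2 has the physician use CGM to guide titration and reduce or stop drugs while the risk persists.
- Section 6.2.2 defers to clinical judgment, and the return sentence is only permissive.
- For high glucose, 6.2.1 allows dose changes and 6.2.3 gives rescue criteria, so nobody is locked out of treatment.

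A reader might therefore go too far the other way and infer that the text sends participants with recent hypoglycemia back to full dose, or denies treatment to those with high glucose. Read as a whole, the documents support neither. It remains true that a dosing safeguard should not depend on the physician noticing that its condition is reversed.

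A charitable reading is that, without hyperglycemia, the drug waits for soft food, and with it the drug may return sooner. That reading still leaves no low-glucose condition and an unexplained difference from Appendix 4.

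On timing, a reader might infer that the Summary's Peri-Procedural Medications row is shown to be the outlier by the Study Design row. That row does defer to Section 6.2.2, but it also speaks of the pre-procedure dose during the transitional diet, which does not fit the reduced first week in 6.2.2.1 either. It is too loose to settle the matter. Section 6.2.1 is better support, although it is a general statement about all background medication.

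A reader might also infer that the Summary's timing cannot apply to re-treated participants, because Appendix 5 cites Section 6. Appendix 5, 4.3.3, refers more broadly to the main protocol's guidelines for management after re-treatment, so the exclusion is not clear-cut.

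**Conclusion.** The condition in 6.2.2.1 is reversed and should be corrected. This rests only on the protocol's own text: the purpose of the section, the neighboring sentence and the Appendix 4 counterpart all point the same way. The practical effect is bounded by the existing safeguards, and the number of participants it can still reach is unknown, with ceilings of 30 index procedures and 30 re-treatments (assuming one per participant). Re-treatment becomes possible only after 48 weeks of follow-up, so the correction can still matter there even if index enrollment has closed.

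The timing mismatch is real but minor. It spans 7 days and produces a conflict only if the drug is returned on days 7 to 13. If index enrollment is complete, it may have little remaining effect.

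**What to change.** In 6.2.2.1, change *hyperglycemia* to *hypoglycemia*, so that the sentence matches Appendix 4, 6.1.2.2. This covers any remaining non-insulin index procedures and, through Appendix 5, re-treatments.

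In the Summary's Peri-Procedural Medications row, state that sulfonylureas and meglitinides may return to the pre-procedure dose from the start of soft food, provided CGM review shows no hypoglycemia. This agrees with 6.2.1, 6.2.2.1 and 6.2.2.2.

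The cost is one word and one Summary row. No data collection is added: under Section 7.10 CGM already runs from Day 1 to Week 4, and 6.2.2.2 already requires its review.

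Moving everything to day 14 instead is not recommended. It would mean revising the Summary's Study Design row, Sections 4.1, 6.2.1 and 6.2.2.1, and Appendix 4, 6.1.2.2; otherwise the two cohorts would follow different rules.

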2.5.2 Anticipated Adverse Events Associated with the DMR Procedure

Anticipated AEs associated with the DMR procedure may include, but are not limited to, the following:

- Complications associated with upper GI endoscopy, including but not limited to, aspiration of gastric contents, aspiration pneumonia
- Complications related to sedation and anesthesia
- Cardiac or respiratory arrest during endoscopy
- Cardiac arrhythmia, muscle spasm, or electrical shock during the procedure
- Death
- Duodenal mucosal inflammation, erythema, erosion, ulcer, bleeding, perforation and their associated complications
- Duodenum motility disorder
- Duodenum stricture and/or obstruction, and their associated complications or interventions
- Excess reduction in oral intake, resulting in dehydration, ketoacidosis, and their associated complications
- GI symptoms post procedure, including nasopharyngeal pain, abdominal pain, cramps, abdominal discomfort, nausea, vomiting, diarrhea, and other GI symptoms
- Inability to endoscopically remove part or all of the device, which may result in the need for surgery
- Infection, systemic or of GI tract, and their associated complications
- Injury to the area of ampulla, leading to biliary and/or pancreatic complications such as biliary obstruction, pancreatitis, etc.

- Injury to peripheral tissue and their associated complications, such as peripancreatic fluid collections, pseudocyst, pancreatic and peripancreatic necrosis, peri-duodenal inflammation or abscess, vascular injuries, pseudoaneurysm, etc.
- Interfere with absorption resulting in nutritional deficiencies
- Undesired metabolic response such as hypoglycemia
- Upper GI tract trauma, including sore or irritated throat, bleeding, perforation, and their associated complications

2.5.3 Residual Risks Associated with the Investigational Device, as Identified in the Risk Analysis Report

Endogenex has conducted extensive assessment of the potential risks associated with the device and its use through Hazard Analysis and FMEA (failure mode and effects analysis) per ISO 14971. A number of safeguards have been built into the device to mitigate high severity risks. The risk assessment concludes that, when used as intended and with mitigation measures implemented, there are no unacceptable risks to the intended patient population.

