6.3. Diabetic Ketoacidosis

Patients with diabetes taking SGLT2i medications may develop diabetic ketoacidosis (DKA) including euglycemic DKA.

Participants treated with SGLT2i who present with signs and symptoms consistent with ketoacidosis, including nausea, vomiting, abdominal pain, malaise, and shortness of breath, should be assessed for ketoacidosis, even if blood glucose levels are below 14 mmol/L (250 mg/dL). If ketoacidosis is suspected, discontinuation or temporary interruption of SGLT2i should be considered and the patient should be promptly evaluated and treated.

Pre-disposing factors to ketoacidosis include a low beta-cell function reserve resulting from pancreatic disorders (e.g. type 1 diabetes, history of pancreatitis, or pancreatic surgery), insulin dose reduction, reduced caloric intake, or increased insulin requirements due to infections, illness or surgery and alcohol abuse.

Participants taking SGLT2i should be educated on DKA risks, common symptoms, and instructed to contact study staff immediately if they experience the above symptoms or risk factors.

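### For the non-insulin cohort, the Protocol Summary omits the SGLT2 inhibitor hold set in Section 6.2.2.1, and its default for unnamed drugs points the other way

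*Protocol*

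**What the plan says.** The Peri-Procedural Medications row of the Protocol Summary sets rules by name for sulfonylureas and meglitinides, metformin, and GLP-1 receptor agonists. For every other glucose-lowering drug it gives one default: "Generally, the dosage of other medications may remain unchanged peri-procedurally unless a hypoglycemic risk is identified by blood glucose monitoring".

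Section 6.2.2.1, the operative text for the non-insulin cohort, adds a rule that the row lacks: "SGLT2i should be held three (3) days prior to the index procedure and resumed when the patient starts soft food". It places the start of soft food at one week after the procedure.

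For the insulin cohort, Section 6.1.2.2 of Appendix 4 says: "The background SGLT2i should be held three (3) days prior to the index procedure and resumed when the patient transitions to soft food". On this class Appendix 4 and Section 6.2.2.1 agree.

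The Study Design row of the same summary does refer the reader to the body: "Background medication(s) may be decreased peri-procedurally per Section 6.2.2 but will be titrated to the pre-procedure dose". The baseline visit (Section 7.12.2) likewise calls for medication management under Section 6 and titration under Section 6.2.

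**The concern.** SGLT2 inhibitors are non-insulin glucose-lowering drugs, and no eligibility criterion for the non-insulin cohort excludes them. Since the summary row does not name them, its default applies to them on a plain reading. A site preparing a participant from that row would find no instruction to hold the drug. A site using Section 6.2.2.1 would stop it three days before the procedure. Two participants in the same cohort could then be managed differently around the intervention that the study is meant to assess for safety, with no protocol deviation evident to either site.

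The difference bears on safety. The protocol lists among the anticipated events of the procedure: "Excess reduction in oral intake, resulting in dehydration, ketoacidosis, and their associated complications". The insulin addendum adds, in its Section 6.3: "Patients with diabetes taking SGLT2i medications may develop diabetic ketoacidosis (DKA) including euglycemic DKA". Neither text says that this is why the drug is held, but together they explain why the difference deserves attention.

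**Working it through.** No sample size, power or error rate is involved. The check is a comparison of texts, plus the length of the hold.

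**Length of the hold under Section 6.2.2.1.** The summary gives the diet steps before soft food: "Patient will be on clear liquid diet for 24 hours, followed by a full liquid diet for 3 days, pureed food for 3 days".
- Procedure to soft food: 1 + 3 + 3 = 7 days. This agrees with the one week stated in Section 6.2.2.1.
- Whole hold: 3 days before + about 7 days after = about 10 days.
- Hold under the summary row, read literally: none.

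**Does the summary's exception cover the hold?** The exception applies only when glucose monitoring shows a hypoglycemic risk. The hold in Section 6.2.2.1 has no such condition and starts before the procedure. The exception therefore cannot produce it.

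**Who is affected?** The Protocol Summary describes the non-insulin population, on one to four non-insulin drugs. Appendix 4, Section 6, takes glucose-lowering medication for the insulin cohort out of the main protocol and states its own rules. The conflict is thus confined to SGLT2 inhibitor users in the non-insulin cohort.

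**Rest of the row against Section 6.2.2.1.**

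| Class | Summary row | Section 6.2.2.1 |
|---|---|---|
| SGLT2 inhibitors | Not named; default of no change | Held from 3 days before until about day 7 |
| Sulfonylureas, meglitinides | Back to the earlier dose after the two-week transitional diet and a CGM review | May return to the baseline dose at soft food, about day 7 |
| GLP-1 receptor agonists | Should be held if nausea or vomiting is significant | May be held in that case |
| DPP-4 inhibitors | Not named; default of no change | May be held, under the same rule as GLP-1 receptor agonists |
| Metformin | Held the day before, resumed with oral intake | Same |

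For sulfonylureas and meglitinides, the full diet lasts 1 + 3 + 3 + 7 = 14 days, so the two texts differ by 14 − 7 = 7 days. Only the metformin rule is the same in both places.

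**The case against.** The best defence is that a summary is not the operative text and that this one sends its reader to the body. The Study Design row cites Section 6.2.2, and the baseline visit cites Sections 6 and 6.2. Re-treatment under Appendix 5 (Section 4.2) also follows Section 6. The default is worded softly, as a general permission, so a specific rule in the body can be read as an exception to it. Section 6.2.2 is itself a guideline that leaves room for clinical judgment.

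Much of this stands. The summary does not order sites to continue the drug, and a site that follows the pointers will find the hold. It cannot be said that a site would miss it. But the pointer in the Study Design row speaks only of decreasing medication, and Section 6.2.1 sends the reader to Section 6.2.2 for drugs with a hypoglycemic risk. Neither prepares the reader for an unconditional hold of a class that the summary row leaves at no change. The conflict is smaller for these pointers, but it remains.

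Three stronger readings are tempting, and the documents do not support them:
- A reader might infer that every SGLT2 inhibitor user in the study is affected. Insulin-cohort users are not, because Appendix 4 governs them.
- A reader might infer that a ketoacidosis precaution has been contradicted. Section 6.2.2.1 gives no reason for the hold and sits under a heading on hypoglycemic risk. The text linking the drug class to ketoacidosis is in the insulin addendum, and the list of anticipated events in Section 2.5.2 names no drug.
- A reader might infer that the primary endpoint is compromised. That needs a missed hold, then an event, then the seriousness criteria of Section 9.1.1, then attribution to device or procedure within 12 weeks. Section 9.2 lists concomitant medication as a ground for judging an event unlikely to be related to the device.

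**Conclusion.** The inconsistency is real and limited. For the non-insulin cohort, the summary row and Section 6.2.2.1 give different peri-procedural instructions on SGLT2 inhibitors, about 10 days of drug apart for each user. The share of users is not stated, so the number of participants exposed cannot be given. The same row also differs from Section 6.2.2.1 on when sulfonylureas and meglitinides are resumed (about 7 days apart) and on how firmly GLP-1 receptor agonists are to be held.

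Any effect on the primary endpoint is only possible. For scale, one additional participant with a qualifying event would move the proportion by 1/20 = 5.0 percentage points with 20 participants, or 1/60 = 1.7 points with 60. Nothing in the documents gives the chance of such an event.

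The conclusion assumes that an unnamed class falls under the row's default, which is the plain reading. It takes no position on which instruction is clinically right; agreement between Section 6.2.2.1 and Appendix 4 does not settle that.

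**What to change.** Reconcile the whole Peri-Procedural Medications row of the Protocol Summary with Section 6.2.2.1, so that each drug class has one instruction wherever it appears. Name SGLT2 inhibitors and DPP-4 inhibitors in the row, or replace the row's drug rules with a direct reference to Section 6.2.2.1. The clinical team must decide each rule. Check the result against Section 6.1.2.2 of Appendix 4, so that any difference between cohorts is deliberate.

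The cost is a wording correction, with the ethics approval that Section 14.1 requires for any amendment. It needs no new data, visits or analyses.
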